All patients should commence assigned treatment as soon as possible and no later than 48 hours (2 calendar days) after randomization.

Stratification Factors

Patients will be stratified according to 3 factors:

- Age: <65 vs. ≥65
- History of hypertension prior to hospitalization: yes vs. no

- Influenza severity scale: 3 vs 4/5

Study site is not a stratification factor because the participating sites will be in close communication to minimize variability in providing BSC. Other potential factors that can influence clinical outcome include COPD, asthma, and cardiovascular disease will be assessed for their relationship to clinical outcome in exploratory analyses.

Blinding

This is a randomized, double-blind study. Patient treatment assignments will remain blinded. The study biostatisticians and clinical research pharmacist may access treatment assignment information as necessary.

The investigational drug blind will be maintained using the IWRS. The drug and placebo injections will be dispensed by the research pharmacy and packaged to be made indiscernible from one another. To maintain the blind, the IWRS will ensure the investigator or designee is unaware of the treatment arm assigned to the subject. Prior to dispensing the study medications, the research pharmacist will verify the appropriate treatment arm assignment using the IWRS cross-referencing the patient's randomization number. The study drug will be delivered to an unblinded administrator of the study drug who is not part of the study team and who will not disclose information regarding study drug administration to any member of the study team, the patient or anyone else.

Unblinding Procedure

The CSPCRPCC will not provide Emergency Code Envelopes to the Research Pharmacy for HITCH. Emergency unblinding will be managed through the 24-hour emergency call service [contact]). This number is also listed on the patient ID cards given to each patient participating in HITCH. The system managed by the CSPCRPCC will electronically capture up-to-date study drug assignment information gathered from the HITCH IWRS.

Authorization to Break the Blind

Under unusual circumstances, chiefly related to patient safety and emergency medical necessity, unblinding may be necessary if knowledge of the study treatment assignment will influence the medical treatment of the patient. This is usually done after consultation with the Study Chair.

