The primary study endpoint will be the composite outcome of mortality, ongoing need for hospitalization, and ECMO or mechanical intubation at 15 days after randomization. This outcome will be compared according to assigned treatment groups, using Pearson χ^2 test. The test for differences between the treatment groups in the primary outcome will be conducted at an overall α -level of 0.05 (i.e. $\alpha = 0.006$ for mid-term interim analysis, $\alpha = 0.044$ for the final analysis). If a patient drops out from the study, then he will be considered as a failure. Additional analyses will be conducted using logistic models to adjust for other clinical factors, such as age, hypertension, and COPD. Logistic regression will be used for the primary endpoint ($y = 1$ if a composite outcome, otherwise $y = 0$) analysis with the treatment group as the testing factor (x). The following covariates will be included in the model: age (z_1), hypertension (z_2), and COPD (z_3), site (z_4). Given the composite outcome probability $p = p(y = 1|x, z_1, z_2, z_3)$, the basic model is defined as follows:

$$\text{Logit}(p) = \ln\left(\frac{p}{1-p}\right) = \beta_0 + \beta_1 x + \beta_2 z_1 + \beta_3 z_2 + \beta_4 z_3$$

Odds ratio and 95% confidence interval (CI) will be presented using SAS PROC GENMOD or PROC LOGSTIC. If the coefficient for treatment effect is significant, then

the null hypothesis will be rejected. Logistic models will be tested for goodness of fit. We will assess goodness-of-fit using the statistic -2 log likelihood, which has a χ^2 distribution under the null hypothesis that all the explanatory variables in the model are zero. We will also consider the Akaike Information Criterion statistic and the Schwartz Criterion statistic, both of which adjust the -2-log likelihood for the number of items in the model. Models that show lack of fit will be reconsidered for the inclusion of additional variables or use of alternate models with assumptions that are better met by the study data. One alternate model if model fit is poor for logistic regression is a log-linear model.

Further, Cochran Mantel-Haenszel method will be used to adjust for three randomization stratification factors (Age: <65 vs. \geq 65, History of hypertension: yes vs. no, and Influenza severity scale: 3 vs 4/5) using SAS PROC FREQ as one of the sensitivity analyses for the primary efficacy endpoint.

Secondary Endpoint Analyses

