Subject disposition will be summarized for the ITT population. The number and percentage of patients who completed or discontinued prematurely from the study by the treatment group will be tabulated and tested using Pearson χ^2 test. The number and percentage of patients who discontinued for each reason will be presented for each intervention group. The number and percentage of patients who completed or discontinued prematurely in each intervention group will also be displayed graphically.

Adherence

Patients who change the treatment groups after randomization or have protocol violations will be identified as non-adherence to the treatment. The number and percentage of non-adherence patients will be summarized by the treatment group and tested using Pearson χ^2 test.

Site Effect

Site effect will be evaluated for four participating sites. Balances of the treatment of assignment and the primary and secondary outcomes will be assessed among the four sites. If there is significant associations between the site and treatment assignment and a study outcome at significance level of 0.05 without multiplicity adjustment, the site effect will be adjusted in the corresponding the primary or any secondary outcome along with the other prognostic factors described in the primary and secondary analyses.

Table 3: Summary of Data Analysis Plan

Endpoint Analyses	Statistical Methods	SAS Procedures
Primary Endpoint A composite endpoint of mortality, hospital stay rate, and ECMO or mechanical intubation at 15 days after randomization	Pearson Chi-square tests or Fisher exact tests Logistic regression adjusted for Age, Hypertension, and COPD	1. PROC FREQ PROC LOGISTC

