#### 3.7.1. Primary Endpoint Analysis

The primary study endpoint will be the composite outcome of mortality, ongoing need for hospitalization, and ECMO or mechanical intubation at 15 days after randomization. This outcome will be compared according to assigned treatment groups, using Pearson  $\chi^2$  test. The test for differences between the treatment groups in the primary outcome will be conducted at an overall  $\alpha$ -level of 0.05 (i.e.  $\alpha = 0.006$  for mid-term interim analysis,  $\alpha = 0.044$  for the final analysis). If a participant drops out from the study, then he will be considered as a failure. Additional analyses will be conducted using logistic models to adjust for other clinical factors, such as age, hypertension, and COPD. Logistic regression will be used for the primary endpoint ( $y = 1$  if a composite outcome, otherwise  $y = 0$ ) analysis with the treatment group as the testing factor ( $x$ ). The following covariates will be included in the model: age ( $z_1$ ), hypertension ( $z_2$ ), and COPD ( $z_3$ ). Given the composite outcome probability  $p = p(y = 1|x, z_1, z_2, z_3)$ , the basic model is defined as follows:

$$\text{Logit}(p) = \ln\left(\frac{p}{1-p}\right) = \beta_0 + \beta_1 x + \beta_2 z_1 + \beta_3 z_2 + \beta_4 z_3$$

Odds ratio and 95% confidence interval (CI) will be presented using SAS PROC GENMOD or PROC LOGSTIC. If the coefficient for treatment effect is significant, then the null hypothesis will be rejected. Logistic models will be tested for goodness of fit. We will assess goodness-of-fit using the statistic -2 log likelihood, which has a  $\chi^2$

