distribution under the null hypothesis that all the explanatory variables in the model are zero. We will also consider the Akaike Information Criterion statistic and the Schwartz Criterion statistic, both of which adjust the -2-log likelihood for the number of items in the model. Models that show lack of fit will be reconsidered for the inclusion of additional variables or use of alternate models with assumptions that are better met by the study data. One alternate model if model fit is poor for logistic regression is a log-linear model. The number and percentage of participants with the composite endpoint at the 15 day after the randomization will be summarized and compared using Pearson  $\chi^2$  test (Table 3.7.1a). For logistic regression analysis, if the coefficient for treatment effect is significant (i.e., the confidence interval for the odds ratio does not include 1), then the null hypothesis will be rejected. The significant level for each covariate coefficient in the model will best determined by Wald test (Table 3.7.1b). Meanwhile, Cochran Mantel-Haenszel test will be used to adjust for three randomization stratification factors (Age: <65 vs.  $\geq$ 65, History of hypertension: yes vs. no, and Influenza severity scale: 3 vs 4/5) using SAS PROC FREQ as one of the sensitivity analyses (Table 3.7.1c).

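### The primary test ignores the randomisation strata and most adjusted models omit baseline severity, which costs some efficiency; separately, the logistic model has its own rule for rejecting the primary null

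*SAP*

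**What the plan says.** **Randomisation.** Protocol section 4 (Stratification Factors) stratifies by age (<65, ≥65), history of hypertension and "Influenza severity scale: 3 vs 4/5".

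**Primary test.** SAP 3.7.1: "This outcome will be compared according to assigned treatment groups, using Pearson" chi-square, with alpha 0.006 at the interim and 0.044 at the final look. SAP 3.9 uses the same test at the interim, with Z boundaries of 2.77 and 0.44. Protocol section 10 adjusts for the stratification factors by CMH only "as one of the sensitivity analyses for the primary efficacy endpoint", and SAP 3.7.1 agrees.

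**Adjusted models.** For the logistic model, SAP 3.7.1 says "The following covariates will be included in the model: age", then hypertension and COPD. Protocol Table 3 lists, for the primary endpoint, "Pearson Chi-square tests or Fisher exact tests Logistic regression adjusted for Age, Hypertension, and COPD". The Cox models in SAP 3.7.2 use the same three covariates, and the mortality logistic and quantile models inherit them by reference. The two proportional-odds models (maximum severity in SAP 3.7.2, oxygen use in SAP 3.7.5) do include the baseline influenza scale.

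**Second rejection rule.** Of the logistic model, SAP 3.7.1 says "If the coefficient for treatment effect is significant, then the null hypothesis will be rejected". It later ties this to the interval: "the confidence interval for the odds ratio does not include 1), then the null hypothesis will be rejected". SAP 3.9 repeats the interval rule for the interim. The only interval level named is 95%.

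**The concern.** Blocking within strata removes between-stratum differences from the treatment comparison. Pearson's variance still counts them, so if the strata are prognostic its true level falls below nominal and power is lost. Severity, which the designers thought important enough to stratify on, is missing from the binary, Cox and quantile models, while COPD, which is not a stratification factor, is included. No reason is given for treating the proportional-odds models differently.

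The logistic sentences raise a different issue. If two tests can each reject the same null, and one of them uses a 95% interval at a look where only 0.006 is to be spent, the overall error rate is no longer controlled at 5%. It is then also unclear which result decides the trial.

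For time to clinical improvement, a two-category decline takes level 3 to 1 and level 4 to 2, both outside hospital. Level 5 can also qualify in hospital by reaching level 3. The endpoint therefore differs in kind by baseline level, yet the log-rank test names no strata.

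**Working it through.** **1. The plan's sample size (Protocol section 10, SAP 2.6).** Inputs: 60% vs 35%, 2:1 allocation, two-sided 0.05, power 90%. Pooled formula, placebo arm, with p̄ = (0.60 + 2×0.35)/3 = 0.4333:

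n = [1.960·√(1.5·p̄(1−p̄)) + 1.282·√(0.24 + 0.2275/2)]² / 0.25² = (1.1895 + 0.7622)² / 0.0625 = 60.9, so 61.

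That gives 61 + 122 = 183, within 3% of the stated 186.

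**2. Unadjusted power at the final look.** Alpha 0.044 gives z = 2.014. At 66/132, the null SE is √(0.2456×(1/66 + 1/132)) = 0.0747 and the alternative SE is √(0.24/66 + 0.2275/132) = 0.0732.

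Power = Φ[(0.25 − 2.014×0.0747)/0.0732] = Φ(1.36) = 91.3%. The same formula gives 89.5% at 62/124, and 64.9% at 66/132 if the effect is 60% vs 42%.

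**3. Why Pearson is conservative: a hand check.** Assume both arms at 60%, half the patients at severity 4/5, severity odds ratio 3, and no effect of the other factors. The stratum rates are then 0.472 and 0.728. Between-stratum variance is 0.128² = 0.0164. Pearson uses 0.24, but under exact balance the relevant variance is 0.24 − 0.0164, a ratio of 0.931. The effective cut-off is 2.014/√0.931 = 2.087, a true two-sided level of 3.7%.

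**4. Simulation at the final look.** The documents give no stratum odds ratios or prevalences, so these are assumed. Setting: n = 198, alpha 0.044, eight strata, 2:1 blocks of 3 and 6, 20,000 trials per cell. Prevalences of age ≥65 / hypertension / severity 4-5 are 50/50/50, 60/60/60 and 65/70/80%.

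| Odds ratios, severity/age/hypertension | Pearson true level | CMH power gain, 60% vs 35% | CMH power gain, 60% vs 42% |
|---|---|---|---|
| none | 4.2-4.5% | about 0 | about 0 |
| 2/1.5/1.2 | 4.0-4.2% | 0.3-0.6 points | 0.9-1.6 points |
| 3/2/1.3 | 3.5-3.7% | 1.1-1.4 | 2.3-3.7 |
| 5/2.5/1.5 | 2.8-3.3% | 1.6-2.3 | 5.0-7.0 |

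CMH's own level was 4.2-4.6%. Repeat runs with prognostic strata widened the Pearson level to 2.6-4.3% and the gain at the planned effect to 2.5 points. An extreme case (severity odds ratio 8, age 3, hypertension 2) gave a Pearson level of 2.1% and gains of 2.7 and about 10 points. I do not rest the point on it.

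**5. Interim look (n = 99, 60% vs 35%).** Chance of crossing 2.77, CMH minus Pearson, in the table's row order: −1.3 to −1.9, −0.2 to +0.6, +1.8 to +3.3 and +4.4 to +7.8 points.

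**6. The second rule.** Z = 2.77 corresponds to a two-sided 0.0056; a 95% interval excluding 1 corresponds to 0.05. Counting a rejection if Pearson crosses its boundary or the logistic interval excludes 1, overall type I error was:
- rule applied at both looks: about 6-9% (separate runs between 5.7 and 8.9%);
- rule applied at the final look only: about 4-6% (3.6 to 6.0%).

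**7. Intubation duration.** If the 11% intubation rate cited in SAP 2.6 applied here, 0.11 × 198 ≈ 22 patients would be intubated. That is too few to justify another covariate without testing.

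**The case against.** Four replies have force.

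- **Pearson is a legitimate choice.** It matches the two-proportion test behind the sample size, and the CMH result will be reported anyway. A reader might infer from the stratification mismatch that the primary test is biased, inflates type I error or leaves the trial underpowered. None of these follows: its error is in the conservative direction and unadjusted power is 91.3%. At the planned effect the CMH gain is small. What stands is that the better-calibrated test is already planned and loses almost nothing at the final look if the strata are not prognostic.
- **The 6-9% depends on a literal reading.** SAP 3.7.1 calls the logistic models additional analyses, and SAP 3.9 ties the termination recommendation to 2.77 and 0.44. A reader might infer that the trial will run at 6-9%. The documents do not settle that, since most of the excess comes from counting the interim logistic interval as a rejection. But nothing withdraws the rejection sentences.
- **Severity could still enter the models.** The covariate list is introduced as examples, and the lack-of-fit clause allows additional variables. That would be a choice made after seeing data, not pre-specification.
- **Time to improvement.** A reader might infer a large power loss from the unstratified log-rank. No figure is supportable: it depends on assumed improvement rates by level and on the planned censoring for worsening and death. Nor must levels 3 and 4 physically leave the building, because Protocol section 2 counts a patient moved to a non-acute unit as discharged.

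**Conclusion.** The concern holds as an efficiency and clarity problem, not a validity problem, and should be fixed. Pearson's true final-look level is about 2.6-4.3% against 4.4% if the strata are prognostic. CMH adds about 0-2.5 points at 60% vs 35% and about 0-7 at 60% vs 42%. These ranges rest on assumed odds ratios (severity up to 5) and prevalences, none of which the documents supply.

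The logistic rejection rule is a separate defect. It is the part that can take overall type I error above 5%: about 6-9% if applied literally at both looks, about 4-6% at the final look only. Omitting baseline severity from the binary logistic, Cox and hospital-stay models is an unexplained inconsistency within the SAP. I attach no power figure to it.

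**What to change.** 1. Make the planned CMH test on the three stratification factors the single deciding primary test at both looks, keeping 2.77, 0.44 and 0.044. Pearson becomes supportive. Report the Mantel-Haenszel stratified risk difference with an interval matched to the final alpha (1 − 0.044 = 95.6%).
2. Replace the logistic rejection sentences (SAP 3.7.1 and 3.9, Protocol section 10) with a statement that the logistic model is supportive and does not reject the primary null.
3. Add the baseline influenza scale (3, 4, 5, as in the maximum-severity model) to the binary logistic, Cox and hospital-stay quantile models. COPD can stay. Leave the intubation-duration model unchanged.
4. Optionally, for time to clinical improvement, add a supportive log-rank test stratified by baseline level 3/4/5. The stratum 3 vs 4/5 would not serve, because it pools level 5 with level 4.

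**Cost.** No new data: the scale is recorded at screening and Day 1 (SAP Appendix 5.3.2). Wording must change together in SAP 3.7.1, 3.7.2, 3.9 and Appendix 5.6 and in Protocol section 10 with Table 3, so a protocol amendment is needed. The same amendment can reconcile site, which Protocol section 10 lists as a logistic covariate but leaves out of its equation.

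**Downsides.** Some strata will be sparse: in the simulations, on average 0.3-6.8 of 99 patients at the interim and 0-6.9 of 198 at the final look fell in strata that add nothing to CMH. If the factors are not prognostic, 1-2 points of interim power are lost.

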### **3.7.2 Secondary Endpoint Analyses**

Secondary endpoints included in the data analysis are the composite outcome of mortality, ongoing need for hospitalization, and ECMO or mechanical intubation at 30 days after randomization, time to clinical improvement, inpatient mortality, length of hospital stay, length of intubation for mechanical ventilation, time to normal temperature, and the maximum severity of COVID-19 illness, which are defined in the endpoint section. The secondary endpoint analyses will be adjusted for multiplicity with a  $\alpha$ -level of 0.0071 for each endpoint.

The composite outcome of mortality, ongoing need for hospitalization, and ECMO or mechanical intubation at 30 days after randomization as a secondary endpoint will be analyzed using the methods described in the primary endpoint analysis (Tables 3.7.2.1a-c).

For the time to clinical improvement as defined by a decline of 2 categories or more from the baseline on the modified 7-category ordinal scale of clinical status of

hospitalized influenza patients (influenza scale, see Appendix 5.1) or hospital discharge (see section 2 for definition of discharge) whichever comes first, survival analysis techniques will be used to analyze the time-to-event data for this endpoint. Participants whose condition worsened, who died, or who withdrew from the study without clinical improvement will be censored. Kaplan-Meier analysis will be used to compare the two curves of the time to the clinical improvement over the patient follow-up time between the two treatment groups and a log-rank statistic will be used to test the equality of the survival function estimates of the two treatment groups using SAS PROC LIFETEST. Kaplan-Meier curves will be created (Figure 3.7.2.1). Additional analysis will be conducted using the Cox's Proportional Hazards model to test the treatment efficacy of the treatment on the time until endpoint events adjusted for three prognostic factors: age, hypertension, and COPD. The hazard ratio and 95% confidence interval (CI) will be presented using SAS PROC PHREG (Table 3.7.2.2). If the coefficient for treatment effect is significant, then the null hypothesis will be rejected. The regression model will be checked for the model assumption, adequacy, and the goodness of fit. If the model shows lack of fit, then alternate models with assumptions that are better met by the study data will be considered.

For mortality endpoint data analysis, the treatment effect will be analyzed initially with a Pearson  $\chi^2$  test (Table 3.7.2.3a) and then logistic regression will be performed using SAS PROC LOGISTIC by taking account of prognostic factors described in the primary endpoint analysis (Table 3.7.2.3b).

For the length of hospital stay data analysis, medians (interquartile ranges) will be presented and Wilcoxon tests, a nonparametric method, will be performed to compare the medians of the length of hospital stay between the two treatment groups using SAS PROC NPAR1WAY (Table 3.7.2.4a). In addition, a quantile regression will be used to test the effect of the treatment on the time until the clinical event adjusted for prognostic factors described in the primary endpoint analysis using a SAS PROC QUANTREG (Table 3.7.2.4b).

For the length of intubation for mechanical ventilation data analysis, medians (interquartile ranges) will be presented and Wilcoxon tests, a nonparametric method,

will be performed to compare the medians of the length of hospital stay between the two treatment groups using SAS PROC NPAR1WAY (Table 3.7.2.5a). In addition, a quantile regression will be used to test the effect of the treatment on the time until the clinical event adjusted for prognostic factors described in length of hospital stay data analysis using SAS PROC QUANTREG (Table 3.7.2.5b).

For time to normal temperature data analysis, survival analysis techniques will be used to analyze the time-to-event data for this endpoint. Participants whose temperature remains abnormal will be censored. Kaplan-Meier analysis will be used to compare the two curves of the time to the clinical improvement over the patient follow-up time between the two treatment groups and a log-rank statistic will be used to test the equality of the survival function estimates of the two treatment groups using SAS PROC LIFETEST. Kaplan-Meier curves will be created (Figure 3.7.2.2). Additional analysis will be conducted using the Cox's Proportional Hazards model to test the treatment efficacy of the treatment on the time until endpoint events adjusted for three prognostic factors: age, hypertension, and COPD. The hazard ratio and 95% confidence interval (CI) will be presented using SAS PROC PHREG (Table 3.7.2.6). If the coefficient for treatment effect is significant, then the null hypothesis will be rejected. The regression model will be checked for the model assumption, adequacy, and the goodness of fit. If the model shows lack of fit, then alternate models with assumptions that are better met by the study data will be considered.

For the maximum severity of COVID-19 illness data analysis, Pearson  $\chi^2$  test will be performed for this categorical endpoint using SAS PROC FREQ initially. Given the endpoint is also an ordinal variable, Cochran–Armitage test will be performed to test the ordinal trend tendency using SAS PROC FREQ (Table 3.7.2.7a). in addition to the frequency analysis, proportional odds logistic regression will also be performed (Table 3.7.2.7b) using SAS PROC LOGISTIC by taking account of the factors of age, hypertension, COPD, and the baseline influenza scale (see Appendix 5.1).

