LOGISTIC by taking account of prognostic factors described in the primary endpoint analysis.

For the length of hospital stay data analysis, medians (interquartile ranges) will be presented and Wilcoxon tests, a nonparametric method, will be performed to compare the medians of the length of hospital stay between the two treatment groups using SAS PROC NPAR1WAY. In addition, a quantile regression will be used to test the effect of the treatment on the time until the clinical event adjusted for prognostic factors described in the primary endpoint analysis.

For the length of intubation for mechanical ventilation data analysis, nonparametric analyses will be performed as described in the length of hospital stay analysis.

For time to normal temperature data analysis, survival analysis techniques will be used as described in the time to the clinical endpoint analysis using SAS PROC LIFETEST and PROC PHREG.

For the maximum severity of COVID-19 illness data analysis, Pearson χ^2 test will be performed for this categorical endpoint using SAS PROC FREQ initially. Given the endpoint is also an ordinal variable, Cochran–Armitage test will be performed to test the ordinal trend tendency using SAS PROC FREQ. in addition to the frequency analysis, proportional odds logistic regression will also be performed using SAS PROC LOGISTIC by taking account of the factors of age, hypertension, COPD, and the baseline influenza scale (see Appendix A).

Exploratory Endpoint Analyses

Clinical and Laboratory Prognostic Factors

Exploratory analyses will be performed to identify the impact of clinical and laboratory prognostic factors on the primary endpoint or any secondary endpoint. Clinical factors include age, presence or absence of COPD, hypertension, or cardiovascular disease, or use of angiotensin converting enzyme inhibitors. Laboratory measurements including D-dimer, IL-6, LDH, ferritin, total WBC, absolute neutrophil count (ANC), absolute lymphocyte count (ALC), and testosterone are measured during the patient's hospital stay. Further germline genomic factors will also be analyzed if feasible as prognostic factors for the study outcomes for part of the patients.

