## 2.6 Sample Size Consideration

In a recent antiviral drug trial to treat adults hospitalized with severe COVID-19 published in the New England Journal of Medicine (NEJM) on March 18, 2020^32, the results showed that a mortality rate of 17%, hospital stay rate of 50%, and ECMO or mechanical intubation rate of 11% among the patients managed with BSC after two-week follow-up. In the current study, we propose a composite endpoint of mortality, ongoing need for hospitalization, and ECMO or mechanical intubation at 15 days after randomization. We are expecting to reduce the composite endpoint rate to 35% after the degarelix treatment plus BSC from 60% for patients treated placebo plus BSC.

The sample size estimation and power analysis shown in Table 2 are based on the hypothesis testing of the primary endpoint, which is the composite endpoint of mortality, hospital stay rate, and ECMO or mechanical intubation at 15 days after

randomization (Day 15). According to the composite endpoint outlined in the previous section, we assume that an effect size for the primary endpoint of 42% can be anticipated in the degarelix group. The other assumptions include a three-month accrual time and one-month follow-up time, and 2:1 sample allocation of degarelix: placebo treatment group. The sample size for the study is estimated based on a superiority trial design. To have 90% power of detecting the expected 42% reduction using a two-sided two proportion test with a significance level of 0.05 in the degarelix compared to the placebo group will require 186 evaluable patients total (i.e. 124 evaluable patients in the degarelix group and 62 evaluable patients in the placebo group). Based on an assumed 5% attrition rate, 198 patients will be required (i.e. 132 in the degarelix group and 66 in the placebo group) to achieve actual statistical significance at alpha level of 0.05 and power of 90% (Appendix 5.5).

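### Length of intubation is summarised by medians and IQRs and modelled by quantile regression, although few men are expected to be intubated: with all men counted the medians are zero, and with only intubated men counted the groups are about 7 against 8 to 15, selected after randomisation

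*SAP*

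**What the plan says.** SAP 3.7.2 opens the paragraph on this endpoint with: "For the length of intubation for mechanical ventilation data analysis, medians (interquartile ranges) will be presented and Wilcoxon tests, a nonparametric method". The same sentence then tells the analyst "to compare the medians of the length of hospital stay between the two treatment groups using SAS PROC NPAR1WAY (Table 3.7.2.5a"), which is the variable of the preceding paragraph. An additional quantile regression by PROC QUANTREG follows (Table 3.7.2.5b), with no quantile named. Protocol Section 10 is shorter: "For the length of intubation for mechanical ventilation data analysis, nonparametric analyses will be performed as described in the length of hospital stay analysis".

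Four other places matter.

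- **Entry status.** The eligibility criteria (Protocol Section 3) admit levels 3 to 5 of the ordinal scale. Invasive ventilation or ECMO is level 6 (SAP Appendix 5.1), so nobody starts intubated.
- **Expected rate.** SAP 2.6 cites, from an earlier antiviral trial, an "ECMO or mechanical intubation rate of 11% among the patients managed with BSC after two-week follow-up". The documents give no other intubation rate.
- **Analysis set.** SAP 3.7 places the secondary analyses on the ITT population and available data. Neither document gives a value for men never intubated, or a rule for this endpoint for men who die or are still intubated at last follow-up.
- **Error rate.** Each of the seven secondary endpoints is tested at 0.0071 (SAP 3.7.2).

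**The concern.** A median describes a duration well when most patients have one. Here most men will have none. The analyst must decide whether a man who was never intubated contributes zero days or is excluded, and the documents do not decide it.

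If he contributes zero, the planned summary prints the same value in both arms, whatever degarelix does, and the adjusted model gives a treatment coefficient of zero. If he is excluded, the comparison loses the protection of randomisation. A drug that prevents the shorter intubations leaves the longer ones behind, so a benefit can look like harm.

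This is one of seven endpoints with its own significance level. Choosing the analysis set after the data are seen would be a post hoc choice on a tested endpoint. The primary endpoint is not affected.

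**Working it through.** **Arm sizes.** The documents give no calculation for this endpoint. The arm sizes come from the primary endpoint (60% against 35%, 2:1, two-sided 0.05, 90% power), which reproduces. The pooled rate is (0.60 + 2 × 0.35)/3 = 0.433. With pooled variance and no continuity correction,

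placebo n = [1.96 × √(0.433 × 0.567 × 1.5) + 1.2816 × √(0.60 × 0.40 + 0.35 × 0.65/2)]² / 0.25² = (1.190 + 0.762)² / 0.0625 = 61.

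The total is 183 against the stated 186, and power at 62 and 124 is 90.5%. The plan randomises 66 and 132.

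**Expected numbers intubated (rate × arm size).**

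| | Placebo (66) | Degarelix (132) |
|---|---|---|
| 11%, no effect on intubation | 66 × 0.11 = 7.3 | 132 × 0.11 = 14.5 |
| 11%, 42% reduction carried over to degarelix | 7.3 | 132 × 0.11 × 0.58 = 8.4 |

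The degarelix rate in the second row is 0.11 × 0.58 = 6.4%. The 42% is the plan's figure for the composite (1 − 35/60), not for intubation.

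**Reading 1: all randomised men, never intubated = 0 days.** The median exceeds 0 only if at least half the arm is intubated, which means 33 of 66 on placebo. At 11% the binomial probability is about 4 × 10⁻¹⁵. In the degarelix arm it is smaller still.

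The 75th percentile exceeds 0 on placebo if at least 17 of 66 are intubated:

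| Placebo intubation rate | P(75th percentile > 0) | P(median > 0) |
|---|---|---|
| 11% | 0.0006 | about 4 × 10⁻¹⁵ |
| 17% | 0.05 | below 10⁻⁸ |
| 20% | 0.15 | below 10⁻⁷ |
| 28% | 0.70 | about 0.0001 |

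The 28% is an upper sensitivity value: 11% plus the 17% mortality, as if every death had been intubated and none was in the 11%. At 11%, Table 3.7.2.5a would therefore show 0 (0 to 0) in both arms. The zero median holds throughout this range; the zero IQR does not.

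I also fitted a median regression with treatment and three covariates to simulated data for 198 men (11% against 6.4% intubated, log-normal durations). The treatment coefficient was zero to numerical precision in each of 50 runs.

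**Reading 2: intubated men only.** About 7 are compared with 8, or 7 with 15. With assumed log-normal durations (SD of the log 0.8), simulated Wilcoxon power at 0.0071 for 7 against 8 is about 4% for a duration ratio of 0.58 and 9% for 0.50. It is 52% even for 0.25.

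On selection, suppose degarelix prevented the shortest 42% of intubations and changed nothing else. The median among those still intubated would move to the 0.42 + 0.58/2 = 0.71 quantile of the untreated distribution. That is a factor exp(0.8 × 0.553) = 1.56, for example from 9 to 14 days. A preventive effect would appear as longer intubation.

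**Wilcoxon test in all 198 men with zeros.** At 11% against 6.4%, with the same assumed durations, simulated power at 0.0071 is about 7%.

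**Deaths.** At the cited 17%, 66 × 0.17 = 11.2 placebo deaths are expected against 7.3 intubations. Any scoring that gives zero days to men who die without intubation gives them the best possible outcome.

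**The case against.** The strongest reply is that the planned test works. SAP 3.3 defines ITT as all randomised men, SAP 3.7 uses that population, and a Wilcoxon test on it is valid, though heavily tied. On that view only a descriptive line and a supplementary model are lost, and the intubated-only comparison is a possible reading, not a planned rule. This stands as far as the test is concerned, and the fix keeps it. It does not rescue the summary or the model, and the phrase about available data leaves the restricted reading open.

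Several stronger statements are tempting, and the documents do not support them.

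- **That the SAP specifies median regression.** It names no quantile. The median is inferred from its wording about comparing medians. A high quantile could show a contrast, but nothing in the plan selects one.
- **That the IQRs must be zero.** The 11% is a two-week rate from another trial, while Protocol Section 5 follows men to Day 60. Once cumulative intubation exceeds about 20%, the upper quartile can no longer be relied on to be zero.
- **That the comparison is fixed at 7 against 8.** That carries the composite's 42% over to intubation; without it the figure is about 7 against 15.
- **That the wrong variable name will mislead the analysis.** The sentence opens with the right one, and the protocol and SAP Appendix 5.6 agree with it. It is a slip to correct.

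It is also fair to say that maximum severity, another secondary endpoint, already compares all men on reaching level 6 or death. Prevention of intubation is therefore not invisible elsewhere in the plan.

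**Conclusion.** The point holds for the summary and the adjusted model, and does not extend to the Wilcoxon test. With all randomised men counted and never-intubated men at zero, both medians are 0 for any plausible rate, and a regression at the median cannot show an effect. The IQRs are also 0 at the planning rate of 11%, but not reliably above about 20%. Restricted to intubated men, roughly 7 are compared with 8 to 15, chosen by a post-randomisation event that is itself part of the primary composite.

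The conclusion rests on the cited 11% being roughly right for this population and on the median being the intended quantile. The power figures rest further on assumed log-normal durations, and the 7% also on a 42% reduction in intubation. This is a should-fix matter for one secondary endpoint and does not touch the primary conclusion.

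**What to change.** Amend the intubation paragraph of SAP 3.7.2 and its table shells, before unblinding, to say the following.

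1. Analyse all randomised men over one stated follow-up window. The sponsor should choose it and reconcile it with Protocol Section 5; the documents give no ground for stopping at Day 30.
2. Score never-intubated survivors as 0 days and rank deaths worst. Ventilator-free days with death scored 0 serves the same purpose, although survivors ventilated throughout would then tie with deaths. State the rule for men still intubated at the end of the window.
3. Make the Wilcoxon rank test the single deciding test at 0.0071.
4. Drop the quantile regression and the median/IQR comparison for this endpoint.
5. Report by arm the percentage ever intubated and the mean days with a bootstrap interval. Give durations among intubated men as description only.
6. Replace length of hospital stay by length of intubation in the text for Table 3.7.2.5a.
7. State that power is low.

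The cost is mainly SAP wording. SAP Appendix 5.3.2 has the ordinal scale completed at each status change, but level 6 pools ECMO with invasive ventilation. The sponsor should therefore confirm that intubation and extubation dates are recorded on some form. The price in interpretation is that the endpoint becomes a combined ranking of death and ventilation. The 7% power applies to days intubated with zeros; power for the death-ranked version was not calculated and should be given when the rule is set.
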